20.3 Analysis Plan

20.3.1 Primary Objectives

20.3.1.1 *To confirm that reducing treatment intensity in non-smoking patients with HPV-related oropharyngeal cancer does not significantly increase the proportion of patients whose tumors recur, compared to our previous experience in similar patients receiving standard-intensity chemo-RT.*

The primary index of recurrence will be the proportion of patients who have local recurrence, distant metastases or second primaries (secondary analyses will be performed on each of these endpoints individually) within two years of the end of treatment. In the primary analysis, *null* hypothesis that the proportion of patients who fail is *greater* than 0.20 will be tested using an exact binomial test (at significance level $\alpha=0.20$). The proportion of patients who recur will be calculated, with a 95% exact binomial confidence interval.

20.3.1.2 *To compare the toxicity in patients receiving reduced intensity treatment to similar patients treated with 7 weeks of chemotherapy concurrent with RT ("standard therapy") in UMCC 2-21.*

Dysphagia and mucositis are measured on continuous scales; there are both observer and patient reports. The null hypothesis of no difference in dysphagia and mucositis at three, twelve and twenty-four months posttreatment between the reduced-intensity therapy versus UMCC 2-21 will be tested ($\alpha=0.20$) in a repeated measures analysis of covariance. In addition, the statistical significance of the difference between the current trial and UMCC 2-21 in the proportions of patients experiencing clinically significant (NCI CTCAE Grade 3 or worse) toxicities will be assessed using Fisher's exact test

(a=0.20).

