20.4.2 Power of primary analysis endpoints

20.4.2.1 The ultimate goal of this research program is to conduct a randomized noninferiority trial to demonstrate that reducing the intensity of therapy in low-risk patients reduces the probability of toxicity while not increasing the probability of tumor recurrence. Such a trial will require hundreds of patients and will be possible only in the cooperative group setting. The purpose of this Phase II trial is to provide preliminary evidence that reduced intensity therapy is practical, and to provide initial evidence of efficacy and toxicity that can be used to design such a trial. The use of the relatively high significance level ($\alpha=0.2$) is not uncommon in early Phase II (e.g., Simon two-stage) trials with limited sample sizes. Out of 33 non-smoking HPV+ patients in the UMCC 2-21 reference set, three patients have died disease-free, and one patient has died from distant metastases. One additional patient in this group has developed a second primary tumor in the oral cavity. All other patients are alive and disease-free. Because the number of events is low, a time-to-event analysis is impractical, and analyses for sub-populations are also unlikely. Because the power will be modest even if the observed failure rates are 2-3 times the control rate, this trial will not definitively test that reduced intensity treatment is as effective as standard chemoradiation, but, if successful, will accrue sufficient data to motivate a true non-inferiority trial.

20.4.2 The power calculations for the toxicity endpoints (Primary Objective 2) will be represented by dysphagia, which is considered the most important. In UMCC 2-21, the patient-reported eating domain score of the HNQOL instrument increased from 10.5 ± 14.9 (mean \pm standard deviation) pre-RT to 25.7 ± 18.9 twelve months after treatment. Videofluoroscopy scores increased from 2.37 ± 1.35 pre-RT to

3.7 ± 1.18 twelve months after treatment. The power of the repeated measures analysis for Primary Objective 2 for these endpoints was assessed by Monte Carlo simulation as the mean twelve month value was reduced from the twelve-month level in UMCC 2-21 (0% decrease) to the baseline UMCC 2- 21 level (100% decrease).

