20.4.3 The hypothesis test for Primary Objective 2 will have at least 80% power for the video fluoroscopy score if the reduced intensity treatment achieves a decrease in dysphagia of 58% or greater compared to UMCC 2-21. The power is somewhat lower for the HNQOL assessment.

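### Primary Objective 2 is answered by at least two toxicity tests, each at alpha 0.20, with no lead instrument, contrast, testing order or error control, and the only model naming mucositis starts at 3 months

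*Combined protocol and SAP*

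**What the plan says.** Section 20.3.1.2 sets out the comparison with UMCC 2-21 for Primary Objective 2. It opens: "Dysphagia and mucositis are measured on continuous scales; there are both observer and patient reports". It then gives two analyses.

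- A repeated-measures analysis of covariance at alpha 0.20, with this hypothesis: "The null hypothesis of no difference in dysphagia and mucositis at three, twelve and twenty-four months posttreatment".
- A Fisher test, also at 0.20, of proportions in the two studies. The plan says that differences in "clinically significant (NCI CTCAE Grade 3 or worse) toxicities will be assessed using" this test.

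The power text in Section 20.4.2 says the toxicity endpoints "will be represented by dysphagia, which is considered the most important". It gives UMCC 2-21 means and SDs for two dysphagia instruments, the HNQOL eating domain and the videofluoroscopy score. On method it says: "The power of the repeated measures analysis for Primary Objective 2 for these endpoints was assessed by Monte Carlo simulation". The quantity changed in that simulation was the mean at twelve months, lowered stepwise towards the pre-treatment value. Section 20.4.3 then states: "The hypothesis test for Primary Objective 2 will have at least 80% power for the video fluoroscopy score" at a decrease of 58% or more, and adds that power is somewhat lower for HNQOL.

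The only sentence on p-value adjustment, in Section 20.2, concerns the early stopping rule.

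On timing, Section 1.0 describes mucositis as acute and dysphagia as late. Section 2.0 puts long-term toxicity first, but also says that acute and long-term sequelae will be graded and compared with the historical control. Section 10.1 collects CTCAE items weekly during treatment and at each follow-up visit to 3 years.

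**The concern.** Section 20.4.3 speaks of one hypothesis test for Objective 2 but attaches two instruments with different power to it. Section 20.3.1.2 contains at least two tests. Neither section says which instrument, which reporter or which contrast (overall group effect, group by visit, or a single visit) decides the objective, or what follows if the results disagree.

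Section 20.4.2 says the trial is meant "to provide initial evidence of efficacy and toxicity that can be used to design such a trial". If videofluoroscopy, patient report and grade 3+ rates point different ways, the plan as written lets the answer be picked after the results are known. The control data already exist, so naming the test beforehand is an important safeguard.

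The timing of mucositis is a second gap. An analysis at 3, 12 and 24 months examines mucositis after the acute phase in which Section 1.0 places it. A reduction in acute mucositis could be missed by the only model that names it.

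**Working it through.** **The plan's own figure.** The stated power is at least 80% for videofluoroscopy at a 58% decrease, that is 0.58 × (3.7 − 2.37) = 0.77 points. The control sample size, within-patient correlation, covariates and contrast used in the simulation are not given, so it cannot be uniquely reproduced. I do not dispute it. The plan states no overall error rate for Objective 2.

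**How many tests.** The smallest permitted reading is two: one joint model and one Fisher test. The text also allows separate models by domain, reporter or instrument. The true number cannot be determined, so the main calculation uses two.

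**Inputs.**
- Alpha 0.20 per test (Section 20.3.1.2), taken as two-sided because the null is no difference.
- 36 current patients (Section 20.1).
- 33 controls. Section 20.4.2.1 gives 33 non-smoking HPV-positive patients in UMCC 2-21. That all 33 have toxicity data is an assumption.
- Common grade 3+ rate 0.1 to 0.5, and correlation between the two test statistics 0 to 0.9. Both are assumptions.

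**Size of Fisher's test.** Summing the null probabilities of all 36 v 33 tables with p ≤ 0.20 gives an actual size s of 0.132 (rate 0.1) to 0.158 (rate 0.3). It is below 0.20 because the test is conservative.

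**Chance of at least one false difference, one model plus Fisher.** If independent, this is 1 − (1 − 0.20)(1 − s):
- s = 0.132: 1 − 0.80 × 0.868 = 0.306
- s = 0.158: 1 − 0.80 × 0.842 = 0.326

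With correlation, the same probability comes from a bivariate normal with matching margins.

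| Correlation | Either direction | Favouring cetuximab |
|---|---|---|
| 0 | 0.306–0.326 | 0.163–0.174 |
| 0.5 | 0.284–0.302 | 0.145–0.154 |
| 0.9 | 0.228–0.238 | 0.115–0.121 |
| One named test | 0.20 | 0.10 |

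**If there were more tests.** Two independent models plus Fisher give 1 − 0.80² × 0.868 = 0.444 to 1 − 0.80² × 0.842 = 0.461. At correlation 0.9 the figure is 0.277–0.283. This only illustrates direction, because the plan does not fix the count.

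**Mucositis, sections side by side.** Section 1.0: acute. Section 2.0: acute sequelae to be compared with the control group. Section 10.1: graded weekly on treatment. Section 20.3.1.2: modelled from 3 months. In the comparison with UMCC 2-21, the weekly grades can therefore enter only through the grade 3+ Fisher test. That test has no stated toxicity list or analysis window. Sections 10.1 and 17.0 give collection periods, from which a window could be inferred but is not declared.

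**The case against.** Much of the case on the other side is fair.

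- **A lead domain exists.** Section 20.4.2 ranks dysphagia first and its simulation varies the twelve-month mean. A reader might infer that the plan sets no priority at all, and that would be wrong. But the ranking serves the power calculation, two instruments remain, and no contrast is carried into the analysis.
- **This is an early phase II trial with a deliberately high alpha.** Section 20.4.2.1 defends 0.20 and disclaims a definitive test. That justifies the level of one test. It does not address several primary tests each at that level.
- **No rule says one significant result is success.** This stands. The error rates show exposure under a rule the plan neither states nor excludes. They are not the trial's type I error. The comparison is also non-randomised, so nominal rates are only a guide.
- **Much higher error rates are tempting.** Counting domains, reporters and visits as separate independent tests produces them, but those counts are assumed, and related measures on the same patients are unlikely to be independent.
- **The acute grades are not unused.** Grade 3+ mucositis on treatment could fall within the Fisher test, and Section 20.3.2.1 relates marker change to the toxicity assessments. Neither is a specified comparison of acute mucositis with UMCC 2-21. The long-term main aim in Section 2.0 explains the late visits, but not the absence of the acute comparison announced there.
- **A missing list and window for grade 3+ is only missing detail.** Taken alone, agreed. It matters here because that test is the only route for on-treatment grades into the comparison.

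**Conclusion.** The point holds. Objective 2 has a lead domain but no lead test: instrument, contrast, order and error control are all undesignated. On the minimum reading of one model plus Fisher, with any single significant result taken as the answer, the chance of a false difference is about 0.23 to 0.33 in either direction, against 0.20. For one favouring cetuximab it is about 0.12 to 0.17, against 0.10. These figures rest on the assumed 36 v 33 patients, grade 3+ rates of 0.1 to 0.5 and correlation from 0.9 down to 0. More tests would raise them.

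Separately, mucositis is modelled only from 3 months, which does not match the plan's own description of it as acute or its announced comparison of acute sequelae.

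A reader might infer that the stated 80% power is wrong or that alpha 0.20 is unjustified. The documents support neither. The plan should be changed, but the defect is one of specification and does not invalidate the design.

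**What to change.** 1. **Name one lead test at the full 0.20.** A suitable choice is the twelve-month group difference in videofluoroscopy score from the planned ANCOVA. It is the measure for which Section 20.4.3 states power and the visit varied in the Section 20.4.2 simulation, and the twelve-month study is already scheduled (Sections 10.2 and 11.0).
2. **Place the other measures.** Either test them after the lead in a fixed order, for example HNQOL eating, then grade 3+ toxicities, then mucositis, each at 0.20 and stopping at the first non-significant result. This holds the overall error at 0.20, because a false claim requires rejecting the first true null in the order. Or report them as secondary with confidence intervals and no pass/fail claim.
3. **Cover acute mucositis.** As a named secondary analysis, compare the worst CTCAE mucositis grade from the start of RT to about 1 month afterwards with UMCC 2-21, if comparable grades exist there. Otherwise report the current trial's grades descriptively. At the same time, state the toxicities and time window of the grade 3+ comparison.

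**Cost.** SAP wording and one check of UMCC 2-21 records, with no new data in the current trial. The demoted measures lose a stand-alone formal claim. Under the fixed order, a miss on the lead test ends formal testing. Missing twelve-month videofluoroscopy studies would matter more.

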In order to reduce dysphagia after chemo-irradiation, in recent years, we have utilized highly conformal radiotherapy (intensity modulated radiotherapy, IMRT) sparing specific anatomical structures, pharyngeal constrictors and the glottic and supraglottic larynx, which we have previously identified as structures whose damage is the likely cause of long-term dysphagia (28). We have demonstrated that it is possible to reduce the doses to these structures without under-treating the target volumes (29). In a phase II study in patients with oropharyngeal cancer treated with chemoRT (weekly carboplatin and taxol concurrent with a 7-week course of IMRT that spared the swallowing structures and delivered a total of 70 Gy tumor dose) we have demonstrated high local- regional tumor control rates (94%) (30). There were no tumor recurrences near the spared swallowing structures in 104 patients. Prospective evaluation of swallowing, including objective studies of swallowing (videofluoroscopy, VF), patient-reported, and observer-rated dysphagia, are encouraging (Feng et al, manuscript in preparation). Notably, strong statistically significant correlations were found between each of the three measures of dysphagia and the doses delivered to the swallowing structures (29, 30). While these relationships do not prove cause-and-effect relationships, they strengthen the hypothesis that reducing the doses to these structures as much as possible can yield clinically significant improvement in dysphagia.

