2.0 STUDY HYPOTHESIS AND RATIONALE

Taking into account the excellent prognosis of patients with HPV-positive oropharyngeal cancer with ≤ 10 pack-year smoking, we hypothesize that reducing the intensity of therapy for these patients will reduce treatment sequelae, notably long-term dysphagia, without affecting their cure rates. The main Aim is to assess whether reducing treatment intensity, by replacing concurrent chemotherapy with cetuximab, will indeed achieve improved long-term toxicity. This Aim will be tested in a prospective study in which acute and long-term sequelae will be graded by observers (using CTCAE v4.0) and by patients (via HN-specific QOL questionnaires). Dysphagia will also be assessed objectively by videofluoroscopy. These measures will be compared to our historical control group (consisting of non-smoking patients with advanced oropharyngeal cancer who received standard-intensity chemo-RT and were evaluated by the same tools on UMCC protocol 2-21). Strict stopping rules will be enacted to ensure that reducing treatment intensity does not increase tumor failures compared with our previous results using standard therapy.

EGFR expression and down-stream signaling will be tested before and after the loading dose of cetuximab (before radiotherapy starts). We hypothesize that in this population with good prognosis, EGFR downstream inhibition after cetuximab test dose will be achieved in the large majority of patients, and that these characteristics will differ significantly from the characteristics of EGFR inhibition which will be observed in poor-prognosis oropharyngeal patients who smoke and/or have HPV- tumors. (These patients will be treated on a different, parallel protocol in which the intensity of therapy will be increased and in whom EGFR level will also be examined before and after a loading dose of cetuximab.)

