8.0 RADIOTHERAPY

- 8.1 Immobilization, imaging and target definitions
 - 8.1.1 The technical details of RT planning will correspond to standard of care at the Department of Radiation Oncology as previously published (29).
 - 8.1.2 Target doses will be similar to the doses delivered in standard practice: 70 Gy at 2.0 Gy/fraction to primary tumor and to lymph nodes with clinical/radiological evidence of metastases, and 56-63 Gy at 1.6-1.8 Gy/fraction to subclinical disease around the primary tumor or to the surgical tumor excision bed, and to the lymph nodes at risk of metastasis, all in 35 fractions, over 7 weeks.
- 8.2 Optimization goals regarding the salivary glands will be:
 - 8.2.1 Mean dose to the parotid glands <26 Gy (at least one gland).
 - 8.2.2 The dose to the volumes of the submandibular glands and oral cavity outside the targets will be minimized.
 - 8.2.3 The doses to the swallowing structures (pharyngeal constrictors, glottic and supraglottic larynx) outside the targets will be minimized, aiming at mean dose < 50 Gy.
- 8.3 OPTIMIZATION CONSTRAINTS WILL BE:
 - 8.3.1 The maximal target PTV dose will be 110% of the prescribed dose.
 - 8.3.2 The minimum target PTV doses will be > 99% of the prescribed dose.
 - 8.3.3 The maximal dose outside the targets will be <105% of the prescribed dose delivered to at least 0.5 cc. volume.
 - 8.3.4 The maximal dose to the spinal cord, expanded 0.5 cm, will be < 50 Gy, to the non-expanded cord < 45 Gy, to the optic pathways < 50 Gy and to the brainstem <54 Gy.

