20.0 STATISTICAL CONSIDERATIONS

20.1 Study Design

This is a Phase II trial of seven weeks RT+cetuximab for head and neck cancer in patients with good prognoses to determine if this treatment will be at least as effective as, but less toxic than, standard therapy. A total of 43 patients will be enrolled in order to obtain 36 patients that complete radiation treatment and have both biopsies taken. Thus, both the clinical primary endpoints and scientific secondary endpoints can be analyzed, as EGFR tumor information is useful for determining potential mechanisms of resistance to cetuximab. Based on the experience of UMCC 9921 and UMCC 2-21, accrual is expected to average one patient per month. To be considered evaluable, a patient must complete the full course of radiation/cetuximab. If radiation and/or cetuximab was stopped or modified due to toxicity, the patient is still evaluable. Inevaluable patients will be replaced.

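### The dysphagia comparison with UMCC 2-21 names no covariates and has no step to detect or adjust for a difference in radiation dose to the swallowing structures

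*Combined protocol and SAP*

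**What the plan says.** The main aim in section 2.0 is causal in form: whether lowering intensity "by replacing concurrent chemotherapy with cetuximab, will indeed achieve improved long-term toxicity". The comparator is not randomised: "These measures will be compared to our historical control group", drawn from UMCC 2-21.

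Section 20.3.1.2 states the test. "The null hypothesis of no difference in dysphagia and mucositis at three, twelve and twenty-four months posttreatment" is tested at alpha 0.20 "in a repeated measures analysis of covariance". No covariate is listed, not even the pre-treatment score, and nothing in section 20 matches on, adjusts for or describes radiation dose.

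The Introduction reports, for the department's own chemo-IMRT work, that "strong statistically significant correlations were found between each of the three measures of dysphagia and the doses delivered to the swallowing structures". It adds at once that this does not prove cause and effect. In the present trial, section 8.2.3 reads "The doses to the swallowing structures (pharyngeal constrictors, glottic and supraglottic larynx) outside the targets will be minimized, aiming at mean dose" below 50 Gy. That is listed as an optimization goal, whereas the limits in section 8.3 are listed as constraints.

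**The concern.** With a historical comparator, a variable strongly related to the outcome and free to differ between cohorts is a natural candidate for confounding. Dose to the swallowing structures fits on the protocol's own account. It is related to the videofluoroscopic, patient-reported and observer-rated measures, and it is a goal whose achieved value can vary with where the target lies. The documents do not hold it equal to UMCC 2-21.

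If mean dose happened to be lower in the new cohort, dysphagia could be lower with no contribution from the drug change, and the test would credit cetuximab. If it were higher, a real benefit could be hidden. Section 20.4.2 calls dysphagia the most important toxicity and says the results will help design a randomised non-inferiority trial, so an error would carry forward. Leaving the covariates open also allows them to be chosen after the data are seen, in a test already set at alpha 0.20.

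**Working it through.** **Inputs from the documents**
- Videofluoroscopy score in UMCC 2-21 (section 20.4.2): 2.37 pre-RT; 3.7 with SD 1.18 at twelve months.
- Stated power (section 20.4.3): at least 80% at a 58% decrease.
- Alpha 0.20 (section 20.3.1.2), read as two-sided because the null is no difference; critical value 1.2816.
- Trial size: "in order to obtain 36 patients that complete radiation treatment and have both biopsies taken" (section 20.1).
- Reference set: 33 non-smoking HPV-positive UMCC 2-21 patients (section 20.4.2). The number with swallowing data is not stated, so 33 is an assumption for this comparison.

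**Assumptions not in the documents**
- Dose-dysphagia correlation r of 0.3 to 0.6. The Introduction says strong but gives no coefficient.
- Mean-dose difference between cohorts, k, of 0.25 to 0.75 SD.

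**1. Target effect and the plan's own power figure.** The target effect is 0.58 × (3.7 − 2.37) = 0.58 × 1.33 = 0.771 points. Comparing twelve-month scores only:
- SE = 1.18 × √(1/33 + 1/36) = 0.284.
- Power = Φ(0.771/0.284 − 1.2816) = 0.92.
- 80% power is reached at (1.2816 + 0.8416) × 0.284/1.33 = 45%.

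This agrees with at least 80% but does not reproduce 58% as the threshold. A change-score comparison with an assumed pre/post correlation of 0.3 gives 0.802, with the threshold at 57.8%. The simulation model and correlation are not given, so the plan's figure can be neither uniquely reproduced nor called wrong. If 58% is the exact 80% point, the implied SE is 0.771/(1.2816 + 0.8416) = 0.363. Both SEs are carried forward.

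**2. Bias with no drug effect.** Bias = r × k × 1.18.
- Mild: 0.3 × 0.25 × 1.18 = 0.09 points, or 11% of 0.771.
- Midpoint: 0.45 × 0.5 × 1.18 = 0.27 points, or 34%.
- Severe: 0.6 × 0.75 × 1.18 = 0.53 points, or 69%.

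**3. Two-sided error rate.** With d = bias/SE, the rate is 1 − Φ(1.2816 − d) + Φ(−1.2816 − d).

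| Case | SE 0.284 (33 vs 36) | SE 0.363 (implied by 20.4.3) |
|---|---|---|
| Mild | d = 0.31; 0.22 | d = 0.24; 0.21 |
| Midpoint | d = 0.93; 0.38 | d = 0.73; 0.31 |
| Severe | d = 1.87; 0.72 | d = 1.46; 0.57 |

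Only one direction favours cetuximab; its nominal share is 0.10. At the midpoint with SE 0.284 that share is 0.36. On that SE, significance needs a difference of 1.2816 × 0.284 = 0.36 points, which is 27% of the 1.33-point rise.

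**4. Power after adjustment.** For one dose covariate, the effective SD is 1.18 × √(1 − r²) × √(1 + pqk²), with pq = 33 × 36/69². At the same 0.771-point effect, power runs from about 0.90 (r = 0.3, k = 1) to 0.98 (r = 0.6, k = 0), against 0.92 unadjusted on the same basis.

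**The case against.** The strongest reply is that radiotherapy was meant to be comparable. Section 8.1.1 ties planning to the department's published standard of care. Section 8.1.2 sets target doses similar to standard practice, 70 Gy in 35 fractions. The Introduction describes an earlier chemo-IMRT series that already spared these structures at the same tumor dose, and section 8.2.3 gives a numeric aim. All of that stands, and it makes a large shift less likely. It does not make achieved doses equal, and the analysis would not show it if they were not.

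Several stronger readings are tempting but unsupported:
- A reader might infer that doses to the swallowing structures were lower in the new cohort. No document reports a difference.
- A reader might infer smaller targets from the exclusion of T4 and N3 in section 4.1. The comparison is with similar UMCC 2-21 patients whose stage mix is not given. The stage III-IV series in the Introduction pools two protocols and is not described as the toxicity comparator.
- A reader might take the correlations as cause. The Introduction disclaims that; adjustment for a prognostic variable does not require it.
- A reader might expect dose adjustment to cure the historical comparison. It deals with measured dose only. Differences in stage, supportive care or rating would remain.

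It is also fair to say that an analysis of covariance may have been meant to include dose, that the gap covers every covariate, and that section 20.4.2 presents the trial as preliminary. These points limit the consequence. They do not supply the missing specification.

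**Conclusion.** The point holds as an omission in the analysis plan. The test for Primary Objective 2 specifies an analysis of covariance without covariates, while the protocol itself identifies a strong correlate of the outcome that is neither fixed nor matched between cohorts. A false-positive result has not been shown; what is shown is that the plan could not tell a dose difference from a drug effect.

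The size depends on the assumed r and k and on a single-timepoint normal approximation. Bias ranges from small (0.09 points) to most of the target effect (0.53 of 0.77). The error rate is barely above nominal at the mild end (about 0.22) and about 0.31 to 0.38 at the midpoint, depending on the SE. The change is worth making because it is inexpensive and the endpoint is the leading toxicity measure.

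**What to change.** In section 20.3.1.2, name the covariates of the dysphagia model for both cohorts: the pre-RT score, planned mean dose to the pharyngeal constrictors, and planned mean dose to the glottic/supraglottic larynx. Use the planned dose from the approved plan, because delivered dose can be altered by toxicity and so by the drug. Tabulate these doses by cohort, and report the unadjusted result beside the adjusted one.

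The documents do not say that UMCC 2-21 plan doses can be retrieved. If they cannot be obtained for all controls, run the dose-adjusted model as a sensitivity analysis in patients with data, and state that the dysphagia difference cannot be attributed to the drug change alone.

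The cost is some plan wording, retrieval of existing planning data, and one or two model degrees of freedom for the dose terms. On the calculation above, little or no power is lost. The adjusted benefit may be smaller than the crude one, and confounding by factors other than dose will remain.
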